9.7.1.8.3 LABORATORY VALUES

Laboratory results will be summarized using Système International units, as appropriate. For all quantitative parameters listed in [Section 9.5.1.4.4](#), the actual value and the change from baseline to each postbaseline visit and to the end of treatment (defined as the last on-treatment value) will be summarized by visit and dose using descriptive statistics. Qualitative parameters listed in [Section 9.5.1.4.4](#) will be summarized using frequencies (number and percentage of subjects), and changes from baseline to each postbaseline visit and to end of treatment will be reported using shift tables. Percentages will be based on the number of subjects with both nonmissing baseline and relevant postbaseline results.

Laboratory test results will be assigned a low/normal/high (LNH) classification according to whether the value was below (L), within (N), or above (H) the laboratory parameter's reference range. Within-treatment comparisons for each laboratory parameter will be based on 3-by-3 tables (shift tables) that compare the baseline LNH classification to the LNH classification at each postbaseline visit and at the end of treatment. Similar shift tables will also compare the baseline LNH classification to the LNH classification for the highest and lowest value during the Treatment Period.

[Appendix 1](#) (Sponsor's Grading for Laboratory Values) presents the criteria that will be used to identify subjects with treatment-emergent markedly abnormal laboratory values (TEMAVs). Except for phosphate, a TEMA is defined as a postbaseline value with an increase from baseline to a grade of 2 or higher. For phosphate, a TEMA was defined as a postbaseline value with an increase from baseline to a grade of 3 or higher. A listing of subjects with markedly abnormal laboratory values will be generated, which will be ordered by dose and subject.

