5.6.3 Laboratory Values

Laboratory results will be summarized using Système International (SI) units, as appropriate. For all quantitative parameters listed in protocol Section 9.5.1.4.4 Safety Assessments (Laboratory Measurements), the actual value and the change from baseline to each postbaseline visit and to the end of treatment will be summarized by visit using descriptive statistics. Qualitative parameters listed in protocol Section 9.5.1.4.4 will be summarized using frequencies (number and percentage of subjects), and changes from baseline to each postbaseline visit and to end of treatment will be reported using shift tables. Percentages will be based on the number of subjects with both nonmissing baseline and relevant postbaseline results.

Laboratory test results will be graded or assigned a low/normal/high (LNH) classification according to whether the value was below (L), within (N), or above (H) the laboratory parameter's reference range. Each laboratory parameter will be assessed based on shift tables that compare the baseline LNH classification to the LNH classification at each postbaseline visit and at the end of treatment.

Appendix 13.2 presents the criteria (based upon Common Terminology Criteria for Adverse events (CTCAE) Version 5.0) that will be used to identify subjects with treatment-emergent markedly abnormal laboratory values (TEMAVs). Except for phosphate, a TEMA V is defined as a postbaseline value with an increase from baseline to a grade of 2 or higher. For phosphate, a TEMA V is defined as a postbaseline value with an increase from baseline to a grade of 3 or higher. A listing of subjects with markedly abnormal laboratory values will be generated, which will be ordered by subject.

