Bilirubin (hyperbilirubinemia)	>ULN – 1.5×ULN if baseline was normal; 1.0 – 1.5×baseline if baseline was abnormal	>1.5 – 3.0×ULN if baseline was normal; 1.5 – 3.0×baseline if baseline was abnormal	>3.0 – 10.0×ULN if baseline was normal; 3.0 – 10.0×baseline if baseline was abnormal	>10.0×ULN if baseline was normal; >10.0×baseline if baseline was abnormal
Calcium, serum-low (hypocalcemia)	<LLN – 8.0 mg/dL <LLN – 2.0 mmol/L Ionized calcium <LLN - 1.0 mmol/L	<8.0 – 7.0 mg/dL <2.0 – 1.75 mmol/L Ionized calcium <1.0 - 0.9 mmol/L; symptomatic	<7.0 – 6.0 mg/dL <1.75 – 1.5 mmol/L Ionized calcium <0.9 - 0.8 mmol/L; hospitalization indicated	<6.0 mg/dL <1.5 mmol/L Ionized calcium <0.8 mmol/L; life-threatening consequences
Calcium, serum-high (hypercalcemia)	>ULN – 11.5 mg/dL >ULN – 2.9 mmol/L Ionized calcium >ULN - 1.5 mmol/L	>11.5 – 12.5 mg/dL >2.9 – 3.1 mmol/L Ionized calcium >1.5 - 1.6 mmol/L; symptomatic	>12.5 – 13.5 mg/dL >3.1 – 3.4 mmol/L Ionized calcium >1.6 - 1.8 mmol/L; hospitalization indicated	>13.5 mg/dL >3.4 mmol/L Ionized calcium >1.8 mmol/L; life- threatening consequences

Sponsor's Grading for Laboratory Values

	Grade 1	Grade 2	Grade 3	Grade 4
Cholesterol, serum-high (hypercholesterolemia)	>ULN – 300 mg/dL >ULN – 7.75 mmol/L	>300 – 400 mg/dL >7.75 – 10.34 mmol/L	>400 – 500 mg/dL >10.34 – 12.92 mmol/L	>500 mg/dL >12.92 mmol/L
Creatinine	>ULN – 1.5×ULN	>1.5 - 3.0×baseline; >1.5 – 3.0×ULN	>3.0×baseline; >3.0 – 6.0×ULN	>6.0×ULN
Fibrinogen plasma-low	>125 - 175 mg/dL	>80 – 125 mg/dL	50- 80 mg/dL	<50 mg/dL
Fibrinogen plasma-high	425 - 500 mg/dL	>500 - 600 mg/dL	>600 - 700 mg/dL	> 700 mg/dL
GGT (γ -glutamyl transpeptidase)	>ULN – 2.5×ULN if baseline was normal; 2.0 - 2.5 x baseline if baseline was abnormal	>2.5 – 5.0×ULN if baseline was normal; >2.5 - 5.0 x baseline if baseline was abnormal	>5.0 – 20.0×ULN if baseline was normal; >5.0 - 20.0 x baseline if baseline was abnormal	>20.0×ULN if baseline was normal; >20.0 x baseline if baseline was abnormal
Glucose, serum-high (hyperglycemia)	Abnormal glucose above baseline with no medical intervention	Change in daily management from baseline for a diabetic; oral antihyperglycemic agent initiated; workup for diabetes	Insulin therapy initiated; hospitalization indicated	life-threatening consequences; urgent intervention indicated

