Glucose, serum-low (hypoglycemia)	<LLN – 55 mg/dL <LLN – 3.0 mmol/L	<55 – 40 mg/dL <3.0 – 2.2 mmol/L	<40 – 30 mg/dL <2.2 – 1.7 mmol/L	<30 mg/dL <1.7 mmol/L life-threatening consequences; seizures
Phosphate, serum-low (hypophosphatemia)	Laboratory finding only and intervention not indicated	Oral replacement therapy indicated	Severe or medically significant but not immediately life-threatening; hospitalization or prolongation of existing hospitalization indicated	life-threatening consequences
Potassium, serum-high (hyperkalemia)	>ULN – 5.5 mmol/L	>5.5 – 6.0 mmol/L	>6.0 – 7.0 mmol/L hospitalization indicated	>7.0 mmol/L life-threatening consequences
Potassium, serum-low (hypokalemia)	<LLN – 3.0 mmol/L	<LLN – 3.0 mmol/L; symptomatic; intervention indicated	<3.0 – 2.5 mmol/L hospitalization indicated	<2.5 mmol/L life-threatening consequences
Sodium, serum-high (hypernatremia)	>ULN – 150 mmol/L	>150 – 155 mmol/L; intervention initiated	>155 – 160 mmol/L hospitalization indicated	>160 mmol/L life-threatening consequences
Sodium, serum-low (hyponatremia)	<LLN – 130 mmol/L	125-129 mmol/L and asymptomatic	<125 – 129 mmol/L symptomatic; 120-124 mmol/L regardless of symptoms	<120 mmol/L life-threatening consequences
Triglyceride, serum-high (hypertriglyceridemia)	150 – 300 mg/dL 1.71 – 3.42 mmol/L	>300 – 500 mg/dL >3.42 – 5.7 mmol/L	>500 – 1000 mg/dL >5.7 – 11.4 mmol/L	>1000 mg/dL >11.4 mmol/L life-threatening consequences

Sponsor's Grading for Laboratory Values

	Grade 1	Grade 2	Grade 3	Grade 4
Uric acid, serum-high (hyperuricemia)	>ULN without physiologic consequences	N/A	>ULN with physiologic consequences	life-threatening consequences

ALT = alanine aminotransferase (serum glutamic pyruvic transaminase), AST = aspartate aminotransferase (serum glutamic oxaloacetic transaminase), N/A = not applicable, LLN = lower limit of normal, ULN = upper limit of normal, WBC = white blood cell.

Based on Common Terminology Criteria for Adverse events (CTCAE) Version 5.0. Published: 27 Nov 2017.

SIGNATURE PAGE

Author:

PPD
Primary Statistician
PPD
Eisai Ltd

Date

Approval:

PPD
PPD
Translational Science Biostatistics
PPD
Eisai Inc.

Date

Study Director

PPD
PPD
Eisai Inc.

Date

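### SAP 5.6.3 drops the protocol's highest/lowest-value laboratory shift tables without declaring it, and does not say how the marked-abnormality flag is set where the grades have no numeric cut-off

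*SAP*

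**What the plan says.** Laboratory parameters are part of the primary safety endpoint (Protocol 9.7.1.1.1; SAP 5.1.2).

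**Shift tables.** Protocol 9.7.1.8.3 classifies each result as low, normal or high (LNH) and plans two kinds of table. One compares baseline with each later visit and with end of treatment. The other compares baseline with the "LNH classification for the highest and lowest value during the Treatment Period". SAP 5.6.3 carries over the first kind only. SAP Section 7 declares no changes to the planned analyses.

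**TEMAV rule.** For every parameter except phosphate, SAP 5.6.3 says a TEMAV "is defined as a postbaseline value with an increase from baseline to a grade of 2 or higher". For phosphate, it "is defined as a postbaseline value with an increase from baseline to a grade of 3 or higher". The grades come from SAP Appendix 13.2, and the subjects identified go into a listing.

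**What remains.** SAP 5.6.3 summarises the value and the change from baseline of every quantitative parameter by visit. SAP Section 5 includes minimum and maximum among the descriptive statistics. Glucose, inorganic phosphorus and uric acid are all in the panel (Protocol 9.5.1.4.4, Table 3).

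**The concern.** There are two separate gaps.

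First, the worst-value shift table is the planned summary that counts each subject once, whenever the abnormality occurred. It also takes in results from any time on treatment, including those outside the visit schedule. Cohort A is treated for 12 + 96 = 108 weeks and Cohort B for 52, so a transient abnormality has many visits at which to occur. Without this table, a reader cannot say how many subjects were ever high or low on a parameter that belongs to the primary safety endpoint. Nor would the reader learn from Section 7 that the table was removed.

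Second, the TEMAV rule is worded as a property of a post-baseline value, but for some analytes the grade depends on treatment, hospitalization or clinical consequences. The SAP does not say which data supply that information. If the flag is programmed from laboratory values alone, these analytes never appear in the listing, and their absence could be taken to mean that nothing marked occurred.

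**Working it through.** The plan states no figure to reproduce here. Three checks apply.

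**1. Can a number alone reach the TEMAV grade?** Appendix 13.2 has 26 rows. Where a row gives both a number and a clinical descriptor, I took the number as sufficient. The rows that fail or overlap are:

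| Row | TEMAV needs | What the grades say | Reached by a number alone? |
|---|---|---|---|
| High glucose | Grade 2 | Grade 1: "Abnormal glucose above baseline with no medical intervention". Grade 2 begins: "Change in daily management from baseline for a diabetic". Grade 3: "Insulin therapy initiated; hospitalization indicated" | No |
| Low phosphate | Grade 3 | Grade 1: "Laboratory finding only and intervention not indicated". Grade 3: "Severe or medically significant but not immediately life-threatening; hospitalization or prolongation of existing hospitalization indicated" | No |
| High uric acid | Grade 2 (marked N/A, so in effect Grade 3) | Grades 1 and 3 are both any value above the upper limit of normal (ULN), separated by physiologic consequences | No |
| Low potassium | Grade 2 | Grades 1 and 2 share the range from the lower limit of normal to 3.0 mmol/L, separated by symptoms and intervention | Only below 3.0 mmol/L, which is Grade 3 |

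The other 26 − 4 = 22 rows reach the TEMAV grade on a number. So 3 of 26 rows cannot be flagged from the value, and 1 of 26 cannot be separated between Grades 1 and 2.

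**2. Can by-visit shifts give the number of subjects ever abnormal?** Let H_j be the number of subjects shifting from normal to high at visit j, with n subjects. The number ever shifting lies between max(H_j) and min(n, ΣH_j). Suppose, for illustration, n = 13 and H_j = 1 at each of three visits. The answer is then anywhere from 1 subject (1/13 = 7.7%) to 3 subjects (3/13 = 23.1%), and the by-visit tables cannot say which. The worst-value table gives the number directly.

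**3. Where does one extreme value show up?** The trace takes one high glucose value in one of 13 subjects who are otherwise normal. The assumed figures, which are not in the documents, are 6 scheduled visits, ULN 6.1 mmol/L and a value of 22 mmol/L. Any value above the ULN gives the same pattern of counts.

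| Output | Value at scheduled visit 3 | Value at an unscheduled visit |
|---|---|---|
| TEMAV from the value alone | 0 | 0 |
| By-visit maximum | 22 at visit 3 | within range at every visit |
| By-visit shift, normal to high | 1 at visit 3 | 0 |
| End-of-treatment shift | 0 | 0 |
| Worst-value shift (protocol only) | 1 | 1 |

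The last column assumes that the unscheduled result is not the last one on treatment and is not mapped to a visit. The SAP gives no rule for unscheduled results, although Protocol 9.5.4.3.2 expects some unscheduled laboratory testing.

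**The case against.** A reader might infer that extreme values of these analytes could be reported as absent. The documents do not support that. With at most 13 subjects, an extreme result at a scheduled visit is normally that visit's minimum or maximum, and it also enters that visit's shift table. Protocol 9.5.1.4.1 further treats a laboratory abnormality as an adverse event (AE) when it leads to intervention, or to withdrawal or withholding of study drug. An untreated abnormality rests on investigator judgment, so this route is only a partial safeguard.

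A reader might also infer that the TEMAV listing is empty for these analytes whatever the data show. That too goes beyond the text. SAP 5.6.3 does not confine grading to the laboratory file, and the study collects medications, AEs and hospitalizations (as serious AEs). Programming rules and table shells sit in separate documents (SAP Sections 9 and 11) that are not available here. For phosphate, Grade 1 itself requires that intervention is not indicated, so a very low value is not automatically Grade 1. What stands is narrower: the SAP does not say how the clinical criteria are applied, and a derivation from values alone would fail.

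It is also fair to say that the scale follows CTCAE version 5.0 and that the three rows are the same in substance in Protocol Appendix 1. Grading by consequence is not an error in itself. Nor would the omitted shift table repair the flag, since LNH classes show direction and not size. The two gaps therefore need separate remedies.

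None of this answers the difference between Protocol 9.7.1.8.3 and SAP 5.6.3, or the statement in SAP Section 7.

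**Conclusion.** The point holds as two limited defects.

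- **Omitted table.** The SAP leaves out a protocol-specified laboratory table for every parameter while declaring no change. The loss is the subject-level count of ever-abnormal results, together with any result not assigned to a scheduled visit. This rests on the SAP text alone; the unseen shells might still contain the table.
- **Unspecified derivation.** For 3 of 26 grading rows the TEMAV flag cannot be derived from the laboratory value, and for low potassium Grades 1 and 2 cannot be told apart by value. The consequence, a listing silent on the first three abnormalities, follows only if the flag is programmed from values alone, which the SAP neither states nor excludes.

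No hypothesis test or decision rule is affected, because the study is descriptive. The point is still worth correcting, because it concerns part of the primary safety endpoint and the remedy is small.

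**What to change.** 1. In SAP 5.6.3, restore the LNH shift tables from baseline to the highest and to the lowest on-treatment value, for all parameters, and state that unscheduled results are included. If the sponsor prefers to omit them, declare the removal with a reason in SAP Section 7.
2. For high glucose, low phosphate, high uric acid and the Grade 1/Grade 2 boundary of low potassium, state that the TEMAV flag is set using the collected AE, concomitant-medication and hospitalization records.
3. For the same analytes, list each treatment-emergent shift out of the reference range in the relevant direction, with the value as a multiple of the reference limit. Add a footnote that absence from the TEMAV listing does not mean absence of a marked abnormality. No outside cut-off is needed.

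Cost: SAP wording and one extra shift table per parameter, which the protocol already specifies. The short listing in item 3 is new and appears in neither document. Item 2 also needs some programming to link laboratory results to clinical records. No additional data collection is required.

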5.6.4 Vital Signs

Descriptive statistics for vital signs parameters (ie, systolic and diastolic BP, pulse, respiratory rate, body temperature, weight) and changes from baseline will be presented by visit.

Vital sign parameter values will also be presented in a listing, ordered by subject.

5.6.5 Electrocardiograms

Shift tables will present changes from baseline in ECG interpretation (categorized as normal; abnormal, not clinically significant; and abnormal, clinically significant) by visit to end of treatment.

5.6.6 Other Safety Analyses

A listing presenting Columbia-Suicide Severity Rating Scale (C-SSRS) assessment results for all subjects will be generated which will be ordered by subject.

5.7 Other Analyses

The presence of anti-E2814 antibodies at various time points postdose will be presented in subject data listings. The number (percentage) of subjects with positive and negative anti-drug antibody (ADA) in serum and plasma will be summarized by visit and dose. A summary table showing ADA subject level status will be presented by dose, together with

summary statistics for the maximum postdose ADA titer value for TE ADA positive subjects. Corresponding tables for neutralizing antibodies (NAb) in serum will be generated as data permit.

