Corrected the PK sampling schedule to reflect that no PK sample is required on Day 84	Corrected for consistency throughout the protocol	Section 9.5.2.1 Section 9.5.1.3.1
Revised the time window allowance for vaccinations relative to dosing, and added instruction for the timing of COVID-19 vaccination relative to dosing	To allow flexibility for subjects to undergo vaccination during ongoing COVID-19 pandemic	Synopsis 
• Concomitant Drug/Therapy Section 9.4.7
Increased the duration of contraception requirement post-dosing and required post-dose interval for reporting pregnancy or breast feeding	To maintain contraception and pregnancy reporting for 5 half-lives after the last dose	Synopsis 
• Exclusion Criteria Section 9.3.2 Section 9.5.4.2
Increased the duration of the post-dose adverse event (AE) follow-up	To continue follow-up of AEs for 5 half-lives after the last dose	Section 9.5.1.4.1
Deleted collection of subjects' dates of birth	For consistency with Eisai Global Protocol template	Section 9.5.1.1.1
Revised the threshold of abnormal hepatic tests that may require reporting and additional evaluation for an underlying etiology	For consistency with Eisai Global Protocol template	Section 9.5.4.3.2
Revised the definition of the Safety Analysis Set for analysis	For consistency with Eisai Global Protocol template	Section 9.7.1.2
Editorial, internal consistency, and formatting revisions	Document quality	Throughout

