9.1.2.3 Follow-Up Period

The Follow-up Period will follow all subjects for a period of 12 weeks after the last dose for safety.

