9.5.1.3 Pharmacokinetic, Pharmacodynamic, Pharmacogenomic, and Other Biomarker Assessments

9.5.1.3.1 PHARMACOKINETIC ASSESSMENTS

The date and time of each sample collection will be recorded. Serum and plasma concentrations of E2814 will be analyzed by population PK analysis to characterize the PK of E2814. (revised per Amendment 03)

Serum, plasma, and CSF concentrations of E2814 will be measured by validated electrochemiluminescence assays and/or by a validated immunoprecipitation/purification followed by liquid chromatography with tandem mass spectrometry, if available. Anti-E2814 antibodies will be measured by a validated electrochemiluminescence assay.

See Laboratory Manual for a description of collection, handling, and shipping procedures for PK samples.

Cohort A

Blood samples (8 mL each, 4 mL for serum and 4 mL for plasma) for PK assessments will be collected according to the following schedule in the Phase 1b Treatment Period (750 mg E2814 administration):

- Predose and immediately at the end of the 1st infusion on Day 1, and at 4, 8, and 24 hours after the end of the infusion
- Single samples will be collected during the outpatient visits on Day 15, Day 29 (predose), and Day 57 (predose).

The following PK samples will be taken during the Phase 2 Treatment Period (1500 mg, 3000 mg, and 4500 mg E2814 administration) (revised per Amendments 01 and 02):

- Predose and immediately at the end of the infusion on Day 85 and at 4, 8, and 24 hours after the end of the infusion
- Predose and immediately at the end of the infusion on Day 169 and predose every 12 weeks thereafter
- Predose and immediately after the end of the infusion on the day of the 1st dose of 4500 mg and predose 12 weeks after the 1st dose of 4500 mg
- At the End of Study/Early Termination and Follow-up Visits (revised per Amendment 03)

CSF samples will be collected via LP predose on Day 1 and Day 84 (Week 12 [this collection can occur on Day 85 as long as it occurs predose]). Thereafter, LP sampling will occur 12 weeks after each dose titration on Day 169 ^{CCI} [REDACTED]

[REDACTED] Day 253 ^{CCI} [REDACTED]

[REDACTED] and the End of Study/Early Termination Visit for PK assessments. (revised per Amendments 01, 02, and 03)

Cohort B

Blood samples (8 mL each, 4 mL for serum and 4 mL for plasma) for PK assessments will be collected at the following timepoints (revised per Amendment 03):

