9.5.1.5 Immunogenicity Assessments

Cohort A

Immunogenicity will be assessed by measuring the presence of anti-E2814 antibodies predose on Days 1, 15, 29, 57, 85, 169 and every 12 weeks thereafter; predose on the day of the 1st dose of 4500 mg and 12 weeks after the 1st dose of 4500 mg; and at the End of Study/Early Termination and Follow-up Visits. (revised per Amendments 02 and 03)

Cohort B

Immunogenicity will be assessed by measuring the presence of anti-E2814 antibodies predose, on Day 1, and at Weeks 12, 24, 36, and at the EOT/ET and Follow-up Visits. (revised per Amendment 03)

CCI

A large rectangular area of the page is completely blacked out, indicating redacted content. The text 'CCI' is visible in red at the top left corner of this redacted area.

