4 DETERMINATION OF SAMPLE SIZE

No formal sample size calculations were performed. For this Phase 1b/2 study, up to 8 subjects in Cohort A and up to 5 subjects in Cohort B were considered adequate to evaluate the initial safety and PK in symptomatic DIAD subjects and to establish evidence of TE.

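### SAP 5.7 sorts ADA results into positive and negative only, with no visible rule for a non-positive result when E2814 is still in the sample

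*SAP*

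**What the plan says.** SAP 5.7 plans listings of ADA results and a two-class table: "The number (percentage) of subjects with positive and negative anti-drug antibody (ADA) in serum and plasma will be summarized by visit and dose". It adds a subject-level ADA status table by dose whose categories are not listed, a summary of the maximum titer in subjects with treatment-emergent ADA, and neutralizing-antibody tables as data permit. It does not define a negative result, names no inconclusive class, and ties no ADA result to a drug concentration.

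On the assay, protocol 9.5.1.3.1 says: "Anti-E2814 antibodies will be measured by a validated electrochemiluminescence assay". No drug tolerance appears in the visible text.

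On sampling, protocol 9.5.1.5 schedules Cohort A for "anti-E2814 antibodies predose on Days 1, 15, 29, 57, 85, 169 and every 12 weeks thereafter", with further samples around the first 4500 mg dose, at End of Study/Early Termination and at Follow-up. Cohort B is sampled "predose, on Day 1, and at Weeks 12, 24, 36, and at the EOT/ET and Follow-up Visits". Protocol 9.1.2.3 fixes the last of these: "The Follow-up Period will follow all subjects for a period of 12 weeks after the last dose for safety".

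On half-life, the Amendment 01 entry in the protocol's Revision History explains the longer adverse-event follow-up this way: "To continue follow-up of AEs for 5 half-lives after the last dose". Protocol 9.5.1.4.1 sets that follow-up at 16 weeks. The Amendment 02 entry on contraception puts 16 weeks and 5 half-lives in the same row.

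Protocol 9.7.1.9 also plans titer categories by visit and dose, and an evaluation of ADA titer against the PK profile. SAP 5.7 contains neither, although SAP 7 reports no changes to the planned analyses.

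**The concern.** Circulating E2814 binds antibodies directed against it. Above a certain concentration, the assay's drug tolerance, those antibodies can go undetected. A non-positive result then means either that there are no ADA or that the assay could not see them. A table with two classes has nowhere to put the second case.

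The table is laid out by dose, which is also the axis along which drug concentration at sampling rises. If tolerance is exceeded at the higher doses, apparent ADA incidence would fall as dose rises because detection falls. Immunogenicity is a secondary objective, and the sample is "up to 8 subjects in Cohort A and up to 5 subjects in Cohort B", so a few results placed in the wrong class change the message.

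**Working it through.** The documents give no ADA rate, drug tolerance or sample-size figure to reproduce; SAP 4 states "No formal sample size calculations were performed". The check is therefore on how much drug each scheduled ADA sample would contain.

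**Inputs**
- Half-life h: 16 weeks = 112 days = 5 half-lives, so h = 112/5 = 22.4 days.
- Sensitivity for h: 100/5 = 20 days (the serious-adverse-event window in protocol 9.5.4.1) and 113/5 = 22.6 days (the on-treatment window in SAP 5.6.2). Both assume that those windows also represent 5 half-lives.
- Doses every 28 days. Cohort A: three each of 750, 1500 and 3000 mg (the shortest permitted steps), then 4500 mg, 27 doses in all with the last on Day 729. Cohort B: 3000 mg, last dose taken as Week 48.
- Assumptions not in the documents: one compartment, linear PK, volume V of 3 to 10 L.

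**Step 1: fraction of a dose remaining, 2^(−t/h), at h = 22.4**
- Next infusion (28 days): r = 2^(−1.25) = 0.420
- Follow-up (84 days = 84/22.4 = 3.75 half-lives): 2^(−3.75) = 0.074

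Over h from 20 to 22.6 days, these are 38 to 42% and 5.4 to 7.6%.

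**Step 2: dose gradient (V cancels)**
- Day 85 predose, after three 750 mg doses: (750/V)(r + r² + r³) = (750/V)(0.672)
- 4500 mg steady-state trough: (4500/V) · r/(1 − r) = (4500/V)(0.726)
- Ratio: 6 × 0.7255/0.6716 = 6.5 (6.3 at h = 20)
- Follow-up after 4500 mg: (4500/V) · r³/(1 − r), which is 192.4/167.9 = 1.15 times the Day 85 trough (131.4/144.2 = 0.91 at h = 20)

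The Follow-up sample after 4500 mg thus carries about as much drug as an on-treatment 750 mg trough. Apart from Day 1 predose, no scheduled sample is drug-free.

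**Step 3: concentrations (µg/mL), C = Σ (dose/V) · 2^(−t/h)**

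| ADA sample | V = 3 L, h = 22.4 | V = 10 L, h = 22.4 | All V (3–10 L) and h (20–22.6 d) |
|---|---|---|---|
| Day 29, first 750 mg trough | 105 | 32 | 28–106 |
| Day 85, after 750 mg | 168 | 50 | 43–170 |
| Day 169, after 1500 mg | 348 | 105 | 89–353 |
| Day 253, after 3000 mg | 697 | 209 | 178–706 |
| 4500 mg trough | 1088 | 327 | 275–1103 |
| Follow-up, Cohort A | 192 | 58 | 39–198 |
| Follow-up, Cohort B | 128 | 39 | 26–132 |

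For subjects dosed as planned, a tolerance below about 26 µg/mL would put every postdose non-positive result in doubt. A tolerance above the 4500 mg trough would put none in doubt. In between, the answer depends on V: at a tolerance of 300 µg/mL, the Day 253 sample exceeds it for V = 3 L (697) but not for V = 10 L (209).

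**Step 4: effect on a small table (illustrative counts)**

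Suppose 1 of 8 subjects is positive and 4 of the other 7 have E2814 above tolerance.
- Two classes: 1/8 = 12.5% (exact 95% CI 0.3 to 52.7).
- Evaluable subjects only: 1/4 = 25.0% (0.6 to 80.6).
- If all 4 doubtful results hid ADA: 5/8 = 62.5%.

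With no positives, the exact upper 95% limit is 36.9% for n = 8, 52.2% for n = 5 and 24.7% for n = 13. Those limits are valid only if every negative is evaluable.

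**The case against.** The strongest objection is that the deciding fact, the assay's drug tolerance, cannot be seen. The text after the ADA schedule in protocol 9.5.1.5 is redacted, as are the synopsis paragraphs on immunogenicity and bioanalytical methods, and any of these could hold a tolerance figure. The assay is described as validated. This stands: understatement of incidence is possible, not shown.

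Three stronger readings are tempting, and the documents do not support them.
- A reader might infer that every non-positive result will be counted as negative. SAP 5.7 does not say so. It names two classes without defining the second, the categories of the subject-level table are not listed, and the programming rules and table shells are in separate documents (SAP 9 and 11).
- A reader might set the modelled levels against the 1.00 µg/mL limit of quantification in SAP 8.1.1. That limit belongs to the E2814 concentration assay and says nothing about interference in the ADA assay.
- A reader might take a falling ADA rate across doses as the mark of interference. In Cohort A the same subjects step up through the doses, so dose is confounded with time and no by-dose pattern isolates a dose effect.

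It can also be said that the analysis is descriptive, and that ADA results and E2814 concentrations are both listed by subject (SAP 5.7 and 5.5.1), so with at most 13 subjects a reader could match them by hand. That lessens the consequence. It does not replace a prespecified rule for the summary tables, and SAP 5.7 itself shows no redaction that could hide one.

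**Conclusion.** The point holds as a conditional gap in a descriptive secondary analysis. Two things are firm. E2814 is present in every scheduled postdose ADA sample of a subject dosed as planned, including Follow-up, where about 7% of the drug remains. And visible SAP 5.7 has no rule for a non-positive result obtained in its presence. The roughly 6.5-fold gradient from the 750 mg to the 4500 mg trough rests on linear PK and the half-life implied by the 16-week window, not on the assumed volume.

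Whether ADA incidence is understated depends on a tolerance that the visible documents do not give: not at all if it exceeds the 4500 mg troughs (about 275 to 1100 µg/mL), for all postdose negatives if it is below about 26 µg/mL. The absolute concentrations rest on the assumed 3 to 10 L. Separately, and without any modelling, SAP 5.7 omits the ADA titer/PK evaluation of protocol 9.7.1.9 while SAP 7 reports no changes.

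**What to change.** In SAP 5.7:
1. State the ADA assay's validated drug tolerance, for serum and plasma separately if they differ.
2. Report three classes, n (%) by visit and dose: positive; negative (no ADA detected and same-visit E2814 at or below tolerance); inconclusive (no ADA detected and E2814 above tolerance). Use the same classes in the subject-level table, with the rule for combining visits written down.
3. Give incidence among evaluable subjects beside the all-subject figure. Both are needed: the first admits positives at any drug level but negatives only at low levels, so it can run high, while the second can run low.
4. State that by-dose ADA rates will not be read as a dose effect, because of the inconclusive results and because dose follows time in Cohort A.
5. Restore the ADA titer/PK evaluation and titer categories of protocol 9.7.1.9, or record their removal in SAP 7.

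The cost is SAP wording, one merge of ADA results with E2814 concentrations and one extra table row. Protocol 9.5.1.3.1 already schedules PK blood at the ADA visits, so no new sample is needed. If no concentration exceeds tolerance, the new row is empty and the negatives are documented as valid. The downside is that fewer subjects may be reportable as ADA-negative.
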